2.1.9 Last contact date

For patients not known to have died at the analysis cut-off, the last contact date will be derived using the last complete date among the following:

Table 2-1 Last contact date data sources

Source data	Conditions
Date of Randomization	No Condition
Last date patient was known to be alive from Survival Follow-up page	Patient status is reported to be alive, lost to follow-up or unknown.
Start/End dates from further antineoplastic therapy	Non-missing medication/procedure term.
Start/End dates from drug administration record	Non-missing dose. Doses of 0 are allowed.
Date of discontinuation/study phase completion from end of treatment disposition page	No condition.
Date of discontinuation/Study phase completion from end of post treatment follow up phase disposition page	No condition
Date of ECG assessment	At least 1 non-missing parameter value
Date of PRO assessment	At least 1 non-missing answer to questionnaire
Tumor (RECIST) assessment date	For non-target lesion: non-missing lesion status For target lesion: non-missing lesion diameter For new lesion: "Is there a new lesion?" yes
Laboratory sample collection date	At least 1 non-missing parameter value

Source data	Conditions
[REDACTED]	[REDACTED]
Vital signs date	At least one non-missing parameter value
Concomitant medication date	At least one non-missing name of medication
[REDACTED]	[REDACTED]
Body fluid/Tissue Collection date	Non-missing result (positive/negative tumor cells)
[REDACTED]	[REDACTED]
Cardiac imaging date	Non-missing LVEF or overall interpretation
Performance Status date	Non-missing performance status
Start/End dates of AE	Non-missing verbatim term

The last contact date is defined as the latest complete date from the above list on or before the data cut-off date. The cut-off date will not be used for last contact date, unless the patient was seen or contacted on that date. No dates post cut-off date will be used. Completely imputed dates (e.g., the analysis cut-off date programmatically imputed to replace the missing end date of a dose administration record) will not be used to derive the last contact date. Partial date imputation is allowed for event (death)/censoring coming from 'Survival information' eCRF.

2.2 Data included in the analysis

The statistical analyses will be performed using all data collected in the database up to the data cutoff date. Any data collected beyond the cutoff date will not be included in the analysis and will not be used for any derivations.

2.3 Analysis sets

2.3.1 Full analysis set (FAS)

The Full Analysis Set (FAS) consists of all randomized patients. Following the intent-to-treat principle, patients will be analyzed according to the treatment and stratum they were assigned to at randomization.

2.3.2 Safety Set

The Safety Set consists of all patients who received at least one dose of any component of study treatment and have at least one post-baseline safety assessment. Patients will be analyzed according to the treatment actually received. Treatment actually received refers to the treatment the patient was randomized to, unless the alternative treatment was received throughout the trial. If a patient takes at least one dose of the randomized treatment then the treatment actually received is the randomized treatment. The statement that a patient has no AE constitutes a safety assessment. Occurrence of a death constitutes a safety assessment as well.

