#### **6.4.1.1 Bisphosphonates and denosumab**

Bisphosphonates and denosumab are generally allowed with the following comments:

- Chronic concomitant bisphosphonate/denosumab therapy for the prevention of bone metastasis is not permitted.
- Bisphosphonate/denosumab therapy for the treatment of osteoporosis is permitted.
- Bisphosphonate/denosumab therapy for the prevention of skeletal related events for patients with bone metastases is permitted.
- If bisphosphonate/denosumab therapy is to be started after the first dose of study drug, prior consultation and approval by Novartis is required and the reason for its use must be clearly documented.

Patients taking concomitant medication chronically should be maintained at the same dose and dose schedule throughout the study period, as medically feasible. [REDACTED]

[REDACTED]

[REDACTED]

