### **10.1.2 Safety set**

The Safety Set includes all patients who received at least one dose of study medication defined as tamoxifen/NSAI, goserelin, LEE011 or placebo. Patients will be analyzed according to the study treatment they actually received. Actual treatment refers to the treatment that the patient was randomized to, unless the alternative treatment was received throughout the trial.

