## **10.3 Treatments (study treatment, concomitant therapies, compliance)**

The safety set will be used for the analyses below.

The actual dose and duration of tamoxifen/NSAI, goserelin, LEE011 and placebo treatment, as well as dose intensity (computed as the ratio of actual dose received to actual duration) and the relative dose intensity (computed as the ratio of the dose intensity to planned dose received/planned duration), will be listed and summarized using descriptive statistics. The total daily doses of tamoxifen/NSAI, goserelin, LEE011 and placebo for each patient will be summarized using descriptive statistics (e.g. mean, median, and mode).

Concomitant medications and significant non-drug therapies will be listed by patient and summarized by ATC (Anatomical therapeutic chemical classification system) term for each treatment group. These summaries will include medications starting on or after the start of study treatment or medications starting prior to the start of study treatment and continuing after the start of study treatment. Any prior concomitant medications or significant non-drug therapies starting and ending prior to the start of study treatment will be listed.

Compliance to the study drug will be assessed by the number of dose reductions and dose interruptions.

The duration of exposure to study treatment and each component of study treatment will also be summarized for the crossover phase in patients who crossed over to LEE011 combination therapy after unblinding (i.e. using the Crossover analysis set).

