2.3.4 Patient classification

Patients may be excluded from the analysis sets defined above based on the protocol deviations entered in the database and/or on specific subject classification rules as defined in [Table 2-1](#).

Table 2-1 Patient classification based on protocol deviations and non-protocol deviation criteria

Analysis set	Protocol deviations leading to exclusion	Non-protocol deviation criteria leading to exclusion
FAS	No written informed consent	NA
Safety set	No written informed consent	No post-baseline safety assessment or no dose of study treatment
Cross-over analysis set	No written informed consent	NA

Withdrawal of Informed Consent

Any data collected in the clinical database after a subject withdraws informed consent from all further participation in the trial, will not be included in the analysis data sets. The date on which a patient withdraws full consent is recorded in the eCRF.

3 Statistical methods used in reporting

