3.6 Concomitant and post-treatment therapy

Concomitant therapies

Concomitant therapy is defined as all interventions (therapeutic treatments and procedures) besides the study treatment that were administered to a patient, coinciding with the study assessment period (even if started before the study assessment period).

Concomitant medications will be coded using the World Health Organization (WHO) Drug Reference Listing (DRL) dictionary that employs the WHO Anatomical Therapeutic Chemical (ATC) classification system.

Concomitant medications will be summarized by lowest ATC class, preferred term and treatment arm. The summary will include medications starting on or after the start of study treatment but no later than 30 days after last dose of study treatment or before the start of open-label ribociclib plus NSAID plus goserelin treatment

The safety set will be used for all concomitant medication tables and listings.

Concomitant medications will be listed also for the cross-over period using the cross-over analysis set. Any concomitant therapies starting more than 30 days after the last date of cross-over open-label study treatment will be flagged in the listing.

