2.3.2 Safety set

The Safety Set consists of all patients who received at least one dose of any component of study treatment. Patients will be analyzed according to the treatment actually received. Treatment

actually received refers to the treatment the patient was randomized to, unless the alternative treatment was received throughout the trial.

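### The final-CSR SAP departs from protocol amendment 7, which it says it follows, on Safety Set membership and on medications ongoing at treatment start, and wrongly states that all its decisions preceded unblinding

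*SAP*

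**What the plan says.** The SAP file holds two plans: one for the primary PFS analysis, based on protocol amendment 4, and one for the final study report (final-CSR SAP), which states in its section 1 that it is based on amendment 7.

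**Safety Set.** Protocol 10.1.2: "The Safety Set includes all patients who received at least one dose of study medication defined as tamoxifen/NSAI, goserelin, LEE011 or placebo". Primary-analysis SAP 2.3.2: "The Safety Set consists of all patients who received at least one dose of any component of study treatment". The final-CSR SAP 2.3.2 instead takes patients who "received at least one dose of any component of study treatment and have at least one post-baseline safety assessment". Its patient-classification table (the second of two numbered 2-1, in section 2.3.4) repeats the condition as an exclusion: "No post-baseline safety assessment or no dose of study treatment". Section 2.3.2 also says that a statement of no AE, or a death, counts as a safety assessment.

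**Concomitant medications.** Protocol 10.3 summarises drugs begun on or after treatment start and also "medications starting prior to the start of study treatment and continuing after the start of study treatment". Primary-analysis SAP 3.7 lists the same two categories. The final-CSR SAP 3.6 says: "The summary will include medications starting on or after the start of study treatment but no later than 30 days after last dose". Two paragraphs earlier it defines concomitant therapy as anything "coinciding with the study assessment period (even if started before the study assessment period").

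**Timing.** Section 1 of the final-CSR SAP says all decisions on the final analysis came before database lock and before the study data were unblinded. Section 1.1 says participants were unblinded under amendment 6. Section 1.2 says PFS and OS had both been tested and reported.

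**The concern.** A plan that names the protocol version it implements should carry that version's definitions or declare where it departs from them. Here one trial would have two Safety Set definitions across its two reports. It would also have two concomitant-medication tables built on different rules under the same title.

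The medication rule matters most in practice. Programmed as written, the final table omits every drug a patient was already taking on day 1 and continued. Bone-modifying agents illustrate this. Protocol 6.4.1.1 says: "If bisphosphonate/denosumab therapy is to be started after the first dose of study drug, prior consultation and approval by Novartis is required". The table would count those later starts and omit use carried over from before treatment.

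The timing sentence matters for transparency. Taken alone, it tells a reader that the plan was fixed blind.

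**Working it through.** There is no stated figure to reproduce. The check sets the current texts side by side, orders the dates, and sizes the possible effect.

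**Membership and medication rules**

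| Rule | Protocol (amendment 7) | Primary-analysis SAP | Final-CSR SAP |
|---|---|---|---|
| Safety Set | One dose (10.1.2) | One dose (2.3.2 and its classification table) | One dose plus a post-baseline assessment (2.3.2 and its classification table) |
| Medication begun before day 1 and continued | Included (10.3) | Included (3.7) | Not in the summary rule, though inside the section's own definition (3.6) |

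The Safety Set condition is operative, because it also stands in the exclusion table. The cross-over set is nested in the Safety Set (final-CSR SAP 2.3.3) and formally inherits it. That can hardly matter there, since protocol 7.1 puts minimum follow-up at 36 months for patients on treatment at amendment 6.

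**Size of the Safety Set effect.** Inputs: 672 randomised 1:1 (final-CSR SAP 1.1), so 672/2 = 336 per arm, assuming equal arms and all dosed. If k dosed patients with no recorded AE are excluded, a percentage x/336 becomes x/(336 − k). The relative rise is 336/(336 − k) − 1 = k/(336 − k):

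- k = 0: 0%
- k = 1: 1/335 = 0.30%
- k = 5: 5/331 = 1.51%

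The documents do not give k.

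**Size of the medication effect.** Let p be the share of on-treatment drugs begun before day 1. The table shows 1 − p of them. The documents do not give p. For assumed values of 10%, 30% and 50%, the table shows 90%, 70% and 50%. This only scales the assumption; the direction is what the text settles.

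**Dates** (protocol, headers and introductions of amendments 6 and 7):

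- PFS primary analysis: October 2017
- OS endpoint met at the second interim analysis: February 2019
- Amendment 6, unblinding: 18-Jul-2019
- Amendment 7, the basis of this SAP: 08-Jan-2020, which is 13 + 31 + 30 + 31 + 30 + 31 + 8 = 174 days later

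The sponsor's clinical team was to run the PFS and interim OS analyses (protocol 10.7.2; primary-analysis SAP 3.14.3). A SAP based on amendment 7 therefore postdates both the sponsor's analyses by arm and the amendment that unblinded participants. The same timing sentence stands in section 1 of the primary-analysis SAP, where it fits, so it was probably carried over.

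**The case against.** The strongest reply is that little follows from any of this.

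- **Safety Set.** To be excluded, a dosed patient would need no AE entry, no statement of no AE, no other post-baseline safety assessment and no death. Few or none will qualify, and nothing in the documents supports k = 5. This stands as a point about size; the conflict in the rule remains.
- **Medications.** Section 3.6 says what the summary will include without saying it includes nothing else, its definition covers earlier starts, and the sentence may be a slip or have lost text. It may well be a slip, but a programmer following the stated rule produces a table that departs from the protocol. It is also true that randomisation ended on 01-Aug-2016, before the primary analysis, so carried-over drugs fell under the primary report's wider rule. The information is not lost to the trial; what suffers is comparability and the final table's own completeness.
- **Timing.** Many rules match the primary-analysis SAP and plausibly were settled blind, and sections 1.1 and 1.2 disclose the unblinding. The sentence nevertheless covers all decisions, and the cross-over rules cannot predate amendment 6. Whether the decisions preceded the final database lock cannot be judged from the documents.
- **Declaration.** The final-CSR SAP's contents list points to a document-history table that is not in the text available. The changes may be declared and justified there, so this point does not claim they are undeclared.

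**Conclusion.** The concern holds in all three parts, on current text alone. The medication rule and the operative Safety Set exclusion carry it; the timing sentence is a lesser correction.

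The Safety Set effect is probably zero or a fraction of one per cent in relative terms, assuming 336 dosed per arm. The medication table is incomplete in a known direction by an unknown amount; AE, laboratory and ECG tables are not touched by that rule. No efficacy conclusion is affected: PFS and OS were already tested, and protocol 10.7.2 makes analyses after amendment 7 descriptive. It is worth correcting because the plan contradicts the protocol it cites, contradicts itself within section 3.6, and misstates its blinding status.

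**What to change.** Four wording changes in the final-CSR SAP:

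1. **2.3.2:** end the membership sentence at the dose requirement, and delete the two sentences on what counts as a safety assessment (no-AE statement; death).
2. **2.3.4, patient-classification table:** leave absence of any dose as the only non-deviation criterion for the Safety Set.
3. **3.6:** add the second category from protocol 10.3, "medications starting prior to the start of study treatment and continuing after the start of study treatment".
4. **Section 1:** say that the plan was finalised before the final database lock (if the sponsor can confirm that) but after the unblinding under amendment 6, and that its analyses are descriptive.

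If the sponsor wants to keep either narrower rule, the alternative is to list it in the SAP as a departure from the protocol with its reason. The cost is text, with the Safety Set flag and the medication table following the corrected rules. No programs are shown, so programming effort cannot be judged.

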2.3.3 Cross-over analysis set

The cross-over analysis set includes all patients in the placebo arm of the Safety set, who elected to cross-over to receive ribociclib combination therapy and received at least one dose of cross-over open-label ribociclib.

2.3.4 Patient classification

Patients may be excluded from the analysis sets defined above based on the protocol deviations entered in the database and/or on specific subject classification rules as defined in [Table 2-1](#).

Table 2-1 Patient classification based on protocol deviations and non-protocol deviation criteria

Analysis set	Protocol deviations leading to exclusion	Non-protocol deviation criteria leading to exclusion
FAS	No written informed consent	NA
Safety set	No written informed consent	No post-baseline safety assessment or no dose of study treatment
Cross-over analysis set	No written informed consent	NA

Withdrawal of Informed Consent

Any data collected in the clinical database after a subject withdraws informed consent from all further participation in the trial, will not be included in the analysis data sets. The date on which a patient withdraws full consent is recorded in the eCRF.

3 Statistical methods used in reporting

3.1 Background and demographic characteristics

The FAS will be used for all baseline disease characteristics and demographic summaries and data listings.

3.1.1 Basic demographic and background data

Qualitative data (e.g., race, ECOG performance status, etc.) will be summarized by means of contingency tables by treatment arm and quantitative data (e.g., age, body weight, etc.) will be summarized by appropriate descriptive statistics (mean, standard deviation, median, minimum, and maximum) by treatment arm.

3.2 Protocol deviation summaries

The number and percentage of patients in the FAS with any protocol deviation will be tabulated by deviation category (as specified in the Study Specification Document) and by treatment arm. Additional protocol deviation summaries will be provided to address the potential impact of COVID-19 pandemic. The number and percentage of patients in the FAS with any protocol

deviation with relationships to COVID-19 will be summarized by deviation category and by treatment arm.

All protocol deviations will be listed.

3.3 Groupings for analysis

The number and percentage of patients in each analysis set (definitions are provided in [Section 2.3](#)) will be summarized by treatment arm.

3.4 Patient disposition

Patient disposition for all randomized patients will be summarized based on FAS. There will be one combined by-treatment summary showing:

1. Number (%) of patients treated/untreated.
2. Number (%) of patients who are still on-treatment (based on the absence of the 'End of treatment' page)
3. Number (%) of patients who crossed over and are still on-treatment (based on the 'Crossover details' page and absence of the 'End of treatment' page)
4. Number (%) of patients who discontinued study treatment (based on the 'End of Treatment' page)
5. Number (%) of patients who crossed over and discontinued study treatment (based on the 'Crossover details' page and the 'End of treatment' page)
6. Reasons for study treatment discontinuation (based on 'End of Treatment' page)
7. Number (%) of patients who entered the post-treatment evaluations (based on 'End of Treatment' page)
8. Number (%) of patients who discontinued from the post-treatment evaluations (based on 'End of post treatment follow up disposition' page)
9. Reasons for discontinuation from the post-treatment evaluations phase (based on 'End of post treatment follow up disposition' page).
10. Number (%) of patients who entered survival follow-up.

3.5 Study treatment

Duration of study treatment exposure, cumulative dose, dose intensity (DI) and relative dose intensity (RDI) will be summarized by treatment. The number of patients with dose reductions/interruptions, and the reasons, will be summarized based on the safety set. Duration of exposure to cross-over open-label ribociclib plus NSAI plus goserelin treatment will be summarized and listed and the number of patients with dose reductions/interruptions and the reasons, will be listed based on the cross-over analysis set.

Details of the derivations and summaries are provided in the following sections.

3.5.1 Duration of study treatment exposure

The duration of exposure to study treatment will be calculated as

Duration of exposure to study treatment (days) = (*last date of exposure* to any study treatment component) – (date of first administration of study treatment) + 1.

Duration of exposure to any single component of study treatment will be calculated as

Duration of exposure (days) = (last date of exposure to study treatment component) – (date of first administration of study treatment component) + 1.

The *last date of exposure* is defined as follows for the study treatment components:

- For ribociclib/placebo, tamoxifen, anastrozole, and letrozole: the last date of exposure is defined as the date of last administration of the corresponding medication;
- For goserelin, the last date of exposure is defined as the date of last administration of goserelin + 27 days.
 - If a patient died or was lost to follow-up within date of last administration + 27 days, then the last date of exposure is the date of death or last contact date, respectively.

The duration of exposure includes the periods of temporary interruption (of any component of the study treatment for any reason). The duration of study treatment exposure will be summarized by treatment arm. In addition, the duration of exposure to study treatment will be categorized into time intervals (e.g., <3 months; 3-<6 months; 6-<9 months, etc); frequency counts and percentages will be presented for the number of patients in each interval.

For analyses related to the cross-over on-treatment period, duration of exposure of cross-over open-label ribociclib plus NSAID plus goserelin treatment will be calculated as above considering the combination of drugs ribociclib plus NSAID plus goserelin administered during the cross-over on-treatment period.

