2.1 Definitions

2.1.1 Study drug and study treatment

Study drug is defined as ribociclib or matching placebo.

Study treatment is defined as ribociclib + (tamoxifen or a NSAI) + goserelin, or matching placebo + (tamoxifen or a NSAI) + goserelin.

Cross-over open-label ribociclib treatment will refer to ribociclib drug administered to patients randomized to placebo plus tamoxifen/NSAI plus goserelin arm who subsequently cross-over to ribociclib plus NSAI plus goserelin (cross-over period).

Cross-over open-label ribociclib plus NSAI plus goserelin treatment will refer to the combination of drugs ribociclib plus NSAI plus goserelin administered during the cross-over period.

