2.1.5 Date of last administration of study treatment

The date of last administration of study treatment is defined as the last date when a nonzero dose of any component of study treatment was administered and recorded on the DAR CRF.

For analyses related to the cross-over period, date of last administration of cross-over open-label ribociclib plus NSAI plus goserelin treatment is defined as the last date when a non-zero

dose of any component of the cross-over open-label ribociclib plus NSAID plus goserelin treatment was administered and recorded on the DAR CRF during the cross-over period.

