2.1.8 On-treatment assessment/event

Safety summaries and selected summaries of deaths will summarize only on-treatment assessments/events.

Double-blind on-treatment period:

An on-treatment assessment/event is defined as any assessment/event in the following time interval:

[date of first administration of study treatment, the earliest between the date of last administration of study treatment + 30 days and the date of first administration of cross-over open-label ribociclib plus NSAID plus goserelin treatment – 1 day], i.e., including the lower and upper limits.

The double-blind on-treatment period is the **default** on-treatment period used in the analyses unless specified otherwise.

Cross-over on-treatment period:

An on-treatment assessment/event is defined as any assessment/event in the following time interval: [date of first administration of the cross-over open-label ribociclib plus NSAID plus goserelin treatment, date of last administration of the cross-over open-label ribociclib plus NSAID plus goserelin treatment + 30 days], i.e., including the lower and upper limits.

(Note: However, the calculation of study treatment duration will use different rules as specified in [Section 3.5.1](#)).

An AE started in the screening phase and ongoing in the on-treatment phase will not be considered as an on-treatment AE unless it has worsened.

If the last date of study treatment is missing, any assessment/event occurring after the start of study treatment will be considered as on-treatment.

Data listings will include all assessments/events, flagging those which are not on-treatment.

Note: The date of first administration of study treatment and the date of last administration of study treatment are defined in [Sections 2.1.4](#) and [2.1.5](#), respectively.

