3.5.2 Cumulative dose and average daily dose

Cumulative dose for any component of study treatment is defined as the total dose of the medication given during the study treatment exposure.

Average daily dose is defined as [Cumulative dose (mg) / Number of dosing days]; drug free day(s) are not counted as dosing days.

Cumulative dose and average daily dose will be summarized using descriptive statistics by treatment arm for each component of study treatment. Patients with no exposure to the study treatment component will be excluded from the corresponding summary.

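### Final-CSR SAP 3.5.1 to 3.5.3 set no stop at crossover, so read literally the placebo-arm exposure and dose summaries include open-label ribociclib treatment

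*SAP*

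**What the plan says.** All references are to the final-CSR SAP (based on protocol amendment 7) unless stated otherwise.

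- **Definitions (2.1.1, 2.1.5).** "Study drug is defined as ribociclib or matching placebo". Crossover treatment has its own name and its own first and last dates, but nothing excludes it from study drug or study treatment. The end date for the whole combination, set in 2.1.5, reads: "defined as the last date when a nonzero dose of any component of study treatment was administered and recorded on the DAR CRF".
- **Duration (3.5.1).** The rule for the oral components is: "For ribociclib/placebo, tamoxifen, anastrozole, and letrozole: the last date of exposure is defined as the date of last administration of the corresponding medication". The injection, given once per 28-day cycle, has a rule of its own: "For goserelin, the last date of exposure is defined as the date of last administration of goserelin + 27 days". The only shortening rule is for death or loss to follow-up shortly after the last goserelin injection. No period restriction is attached to the reporting: "The duration of study treatment exposure will be summarized by treatment arm". A closing paragraph adds a separate duration for the crossover period.
- **Dose (3.5.2, 3.5.3).** "Cumulative dose for any component of study treatment is defined as the total dose of the medication given during the study treatment exposure". DI divides cumulative dose by component exposure, adjusted for planned off-days in the case of ribociclib/placebo. RDI divides DI by the planned intensity, 600 mg/day for ribociclib/placebo.
- **Safety window (2.1.8).** The default on-treatment period ends 30 days after last study treatment or on the day before first crossover treatment, whichever is earlier. A note, pointing to 3.5.1, adds: "However, the calculation of study treatment duration will use different rules as specified in".
- **Neighbouring sections.** Dose changes (3.5.4), component discontinuation (3.5.5), concomitant medication (3.6) and safety (3.7) are each limited to the double-blind period or cut at crossover.

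**The concern.** Three adjoining sections lack the limit that the sections after them have. NSAI and goserelin continue through crossover, and crossover ribociclib meets the definition of study drug. On the plain wording, the last dose for a placebo patient who crossed over is therefore a crossover dose. Her placebo-arm duration, cumulative dose, average daily dose, DI and RDI would then describe a mixture of placebo and active drug. The AE, laboratory and concomitant-medication tables for the same arm stop at crossover, so exposure and safety would cover different periods within one report. Two programmers could also produce different tables from the same text.

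**Working it through.** **1. Side-by-side reading.** Sections 3.5.1 to 3.5.3 repeat sections 3.6.1 to 3.6.3 of the primary-analysis SAP almost unchanged. That SAP predates crossover and needed no limit. In the final-CSR version, 3.5.1 gained only the paragraph on crossover exposure, whereas 3.5.4 to 3.7 were revised to add a limit. The disposition list (3.4) counts patients who crossed over and then stopped study treatment, so the SAP itself carries that term through crossover.

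**2. The SAP's own formula.** With D1 the ribociclib/placebo duration in days, adjusted duration is D = 21 x [D1/28] + min(21, D1 - 28 x [D1/28]). All six worked examples in 3.5.3 reproduce: 66 gives 52, 108 gives 84, 30 gives 23, 7 gives 7, 22 gives 21, and 28 gives 21.

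**3. One illustrative patient (assumed).** She takes placebo + NSAI + goserelin for 36 cycles, then has 12 crossover cycles. A month is 30.4375 days.

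- Duration stopped at crossover: 36 x 28 = 1,008 days = 33.1 months.
- Literal duration: 48 x 28 = 1,344 days = 44.2 months. The extra 336 days (11.0 months) also appear in the crossover duration summary.
- Ribociclib/placebo cumulative dose: 36 x 21 x 600 = 453,600 mg stopped; 453,600 + 12 x 21 x 600 = 604,800 mg literal.
- RDI: unchanged at 100% if crossover dosing stays at 600 mg/day. If crossover dosing were 400 mg/day throughout, literal RDI is (453,600 + 12 x 21 x 400) / 1,008 / 600 = 554,400 / 1,008 / 600 = 91.7%, against 100% when stopped.

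**4. Effect on the arm mean.** The inputs are:

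- 672 randomized 1:1 (1.1), taken as 336 per arm.
- 8 crossovers among the 35 placebo-arm patients still on treatment on 08-Jan-2020 (protocol, Amendment 7).
- An assumed 12 to 36 months of crossover treatment each.

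Shift in mean = crossovers x months / 336:

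- 8 x 12 / 336 = 0.29 month
- 8 x 36 / 336 = 0.86 month

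The 8 patients are 8 / 336 = 2.4% of the arm, so the median hardly moves. They already belong to the long tail, because follow-up for patients on treatment at Amendment 6 was at least 36 months (protocol 7.1). The maximum and the top duration categories therefore move most.

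The final number of crossovers is not in the documents. The 46 placebo-arm patients still on treatment on 03-Jul-2019 (protocol, Amendment 6) give a ceiling: 46 x 12 / 336 = 1.64 months and 46 x 36 / 336 = 4.93 months.

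**5. Why a simple date cap is not enough.** Suppose the rule were the earlier of the present end date and the day before first crossover ribociclib. Take a tamoxifen patient with 36 full placebo cycles, followed by the 35-day washout described in the protocol. The ribociclib/placebo component would end on day 1,008 + 35 = 1,043. Then D = 21 x 37 + 7 = 784 and RDI = 453,600 / 784 / 600 = 96.4%, although she missed no placebo dose. Ending at her last non-zero placebo dose (day 35 x 28 + 21 = 1,001) gives D = 756 and RDI = 100%.

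Goserelin raises a similar issue. With 38 injections up to day 1,037, the existing denominator gives 38 x 3.6 / (1,064 / 28) = 3.6 mg/28 days. Truncating it at day 1,043 gives 136.8 / 37.25 = 3.67, an RDI of 102%.

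**The case against.** The best defence is that the SAP implies the limit. Section 2.1.1 names crossover treatment separately, 2.1.2 to 2.1.5 give it its own dates, 2.1.8 makes the double-blind period the default, and 3.5.1 ends with a rule for the crossover period. An unlabelled rule could then be taken to mean double-blind treatment. Programming specifications that are not part of these documents may already say so. This is a fair account of the likely intent, and it stands to that extent. It does not settle the text: no sentence excludes crossover dosing, and 3.4 uses study treatment across crossover.

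Four stronger readings are tempting, and the documents do not support them.

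- A reader might infer that the note in 2.1.8 deliberately lifts the crossover cap for duration. The same note stands in 2.1.8 of the primary-analysis SAP, where no crossover existed. There it can only separate the 30-day safety tail from the exposure end dates.
- A reader might infer that cumulative dose and DI are also reported twice. Section 3.5 plans a crossover summary of duration only.
- A reader might infer that the tamoxifen washout is tabulated as a dose interruption. Section 3.5.4 is limited to the double-blind period and does not count an interruption without a resumed dose. The resumed dose here falls outside that period.
- A reader might infer that the AE comparison uses a wrong denominator. The AE summaries in 3.7.1 are numbers and percentages of patients, and no exposure-adjusted rates are planned.

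**Conclusion.** The omission is real and confined to 3.5.1 to 3.5.3. As written, those sections put open-label crossover treatment into the placebo-arm duration, cumulative dose, average daily dose, DI and RDI, and the crossover months are summarized in two places. Under the stated assumptions (8 crossovers, an even split, 12 to 36 crossover months each) the mean rises by about 0.3 to 0.9 month. RDI shifts only for patients whose crossover dose is reduced or who have a gap before crossover. No AE percentage changes, and the PFS and OS tests, already reported, are untouched. This is a small descriptive inconsistency, worth correcting because it is cheap to remove and otherwise leaves the tables to the programmer's interpretation.

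**What to change.** In 3.5.1 to 3.5.3, state that for placebo-arm patients who crossed over, the last date of exposure and all dose totals use only dosing records dated before the first crossover open-label ribociclib dose. Then specify:

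- The ribociclib/placebo component ends at the last non-zero placebo dose, so a drug-free gap or washout is not counted as exposure.
- Overall duration and goserelin duration (last injection + 27 days) are truncated at the day before first crossover ribociclib.
- Goserelin DI keeps its + 27-day denominator, counted from the last injection before crossover.

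Section 3.5.4 needs no change on this point. The cost is a short SAP clarification, one derivation rule and a rerun of the affected exposure tables. No new data are required.
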